4.1.5 Blinding and procedures for unblinding

4.1.5.1 Blinding

Patients, investigators, central reviewers, and everyone involved in trial conduct or analysis or with any other interest in this double-blind trial will remain blinded with regard to the randomised treatment assignments until a snapshot after Last Patient Last Visit Primary Endpoint is taken. This snapshot will be taken after the last patient completes the EOT Visit, and will be used to obtain efficacy results, to guide further development plans for BI 764198. At the timepoint of unblinding of this snapshot, patients and investigators will continue to be blinded and will remain so until after database lock after Last Patient Completed.

The access to the randomisation codes will be kept restricted by the global Randomization Team (gRT) until the last patient has completed their End of Treatment (EOT) visit and all data up until that time point should be entered and cleaned and in preparation for unblinding according to the sponsor's Standard Operating Procedures (SOPs).

To ensure that all members of the Trial Team remain blinded, a trial independent statistician (iSTAT) will be appointed for the DMC. The iSTAT is involved neither in the conduct of the trial(s) the DMC Charter refers to, nor in any other project activities. The iSTAT is not allowed to disclose any unblinded trial data to anyone else other than the DMC members and is also not allowed to disclose any of the proceedings of the closed DMC session to non-DMC members. In order to unblind the data for the DMC, the randomization codes will be submitted to the iSTAT by the gRT according to the sponsor's SOPs.

Refer to [Section 4.1.5.2](#) for rules of breaking the code for an individual or for all patients in emergency situations.

4.1.5.2 Unblinding and breaking the code

Emergency unblinding will be available to the investigator via IRT. It must only be used in an emergency situation when the identity of the trial drug must be known to the investigator

Proprietary confidential information © 2021 Boehringer Ingelheim International GmbH or one or more of its affiliated companies

in order to provide appropriate medical treatment or otherwise assure safety of trial participants. The reason for unblinding must be documented in the source documents and/or appropriate CRF page.

Due to the requirements to report Suspected Unexpected Serious Adverse Reactions (SUSARs), it may be necessary for a representative from [REDACTED] to access the randomisation code for individual patients during trial conduct. The access to the code will only be given to authorised Pharmacovigilance representatives for processing in the PV database system and not be shared further.

4.1.6 Packaging, labelling, and re-supply

The investigational medicinal products will be provided by BI or a designated clinical research organization (CRO). They will be packaged and labelled in accordance with the principles of Good Manufacturing Practice (GMP). Re-supply to the sites will be managed via an IRT system, which will also monitor expiry dates of supplies available at the sites. For details of packaging and the description of the label, refer to the ISF.

4.1.7 Storage conditions

Drug supplies will be kept in their original packaging and in a secure limited access storage area according to the recommended storage conditions on the medication label. Where necessary, a temperature log must be maintained for documentation.

If the storage conditions are found to be outside the specified range, the Clinical Research Associate CRA (as provided in the list of contacts) must be contacted immediately.

4.1.8 Drug accountability

The investigator or designee will receive the investigational drugs delivered by the sponsor when the following requirements are fulfilled:

- Approval of the clinical trial protocol by the IRB / ethics committee,
- Availability of a signed and dated clinical trial contract between the sponsor and the investigational site,
- Approval/notification of the regulatory authority, e.g. competent authority,
- Availability of the curriculum vitae of the Principal Investigator,
- Availability of a signed and dated clinical trial protocol,
- Availability of the proof of a medical license for the Principal Investigator,
- Availability of FDA Form 1572 (for US sites).

Investigational drugs are not allowed to be used outside the context of this protocol. They must not be forwarded to other investigators or clinics.

The investigator or designee must maintain records of the product's delivery to the trial site, the inventory at the site, the use for each patient, and the return to the sponsor or warehouse / drug distribution centre or alternative disposal of unused products. If applicable, the sponsor or warehouse / drug distribution centre will maintain records of the disposal.

Proprietary confidential information © 2021 Boehringer Ingelheim International GmbH or one or more of its affiliated companies

These records will include dates, quantities, batch / serial numbers, expiry ('use- by') dates, and the unique code numbers assigned to the investigational medicinal product and trial patients. The investigator or designee will maintain records that document adequately that the patients were administered the doses specified by the Clinical Trial Protocol (CTP) and reconcile all investigational medicinal products received from the sponsor. At the time of return to the sponsor and/or appointed CRO, the investigator or designee must verify that all unused or partially used drug supplies have been returned and that no remaining supplies are in the investigator's possession.

4.2 OTHER TREATMENTS, EMERGENCY PROCEDURES, RESTRICTIONS

4.2.1 Other treatments and emergency procedures

[figure not shown]
There are no special emergency procedures to be followed.

Study medication will be administered as an add-on to standard of care (SoC). The SoC will be based on appropriate guidelines in place at the time of treatment and may change during the course of the study as new information becomes available about treating COVID-19.

4.2.2 Restrictions

4.2.2.1 Restrictions regarding concomitant treatment

The medications listed under the exclusion criteria ([Section 3.3.3](#)), are restricted during the trial (refer to ISF for further details).

4.2.2.2 Restrictions on diet and life style

Patients are hospitalised during the treatment period and study drug should be administered after at least 6 hours fasting (no food, water allowed). Patients should remain fasted for 1.5 hours after study drug administration.

4.2.2.3 Contraception requirements

WOCBP (for the definition please refer to [Section 3.3.3](#)) and men able to father a child must abstain from male-female sex or must use highly effective methods of birth control per ICH M3 (R2) that result in a low failure rate of less than 1% per year when used consistently and correctly during hospitalisation and for a period of at least 7 days after last trial drug intake.

Men (trial participant or partner of a trial participant) must be vasectomised with documented absence of sperm or use a condom if their sexual partner is a WOCBP.

WOCBP (trial participant or partner of a trial participant) must use a highly effective method of birth control per ICH M3 (R2) that results in a low failure rate of less than 1% per year when used consistently and correctly if their sexual partner is a man able to father a child.

- Combined (estrogen and progestogen containing) hormonal birth control that prevents ovulation (oral, intravaginal, transdermal).
- Progestogen-only hormonal birth control that prevents ovulation (oral, injectable, implantable).
- Intrauterine device (IUD) or intrauterine hormone-releasing system (IUS).
- Bilateral tubal occlusion

Or WOCBP and men able to father a child must abstain from male-female sex. This is defined as being in line with the preferred and usual lifestyle of the patient or, per investigator judgement, relevant to the patient during hospitalisation through 7 days after last trial drug intake. Periodic abstinence e.g. calendar, ovulation, symptothermal, post-ovulation methods; declaration of abstinence for the duration of exposure to study drug; and withdrawal are not acceptable.

4.3 TREATMENT COMPLIANCE

For each dose of study medication administered, the date, time, and route will be entered into the electronic case report forms (eCRFs). Any missed doses must be recorded in the eCRFs.

5. ASSESSMENTS

5.1 ASSESSMENT OF EFFICACY

5.1.1 Proportion of patients alive and free of mechanical ventilation at Day 29

Patients who are alive and free of mechanical ventilation at Day 29 is defined as those who have not died at Day 29 and those who do not depend on mechanical ventilation for breathing at Day 29.

5.1.2 Improvements on the WHO Clinical Progression Scale

The condition of each potential participant in the study will be assessed using the WHO Clinical Progression Scale at the time points specified in the [Flow Chart](#), prior to study drug administration as applicable.

WHO Clinical Progression Scale [R20-2002]:

0. Uninfected; no viral RNA detected
1. Asymptomatic; viral RNA detected
2. Symptomatic; independent
3. Symptomatic; assistance needed
4. Hospitalised; no oxygen therapy
5. Hospitalised; oxygen by mask or nasal prongs
6. Hospitalised; oxygen by non-invasive ventilation or high flow
7. Intubation and mechanical ventilation, $pO_2/FiO_2 \geq 150$ or $SpO_2/FiO_2 \geq 200$
8. Mechanical ventilation $pO_2/FiO_2 < 150$ ($SpO_2/FiO_2 < 200$) or vasopressors
9. Mechanical ventilation $pO_2/FiO_2 < 150$ and vasopressors, dialysis, or extracorporeal membrane oxygenation (ECMO)
10. Death

To be considered for inclusion in the study, patients must be Grade 5 or 6 on this scale.

To be considered a “responder” to treatment with a target candidate, a patient needs to show a response defined by time to an improvement of at least 2 points (from randomisation) on this scale by Day 29. For example, a patient who is Grade 5 (hospitalised; oxygen by mask or nasal prongs) at randomisation but improves to Grade 3 (symptomatic; assistance needed) would be considered to be a responder. A patient with a discharge from hospital or who is considered fit for discharge (a score of 0, 1, or 2 on the Clinical Progression Scale) by Day 29 will also be considered to be a responder.

5.1.3 Other efficacy assessments

The duration of, and time to, ICU admission, the number of ventilator-free and oxygen-free days, the initiation of new ventilation use, and duration of hospitalisation will be derived from source documents. The date of discharge from hospital and/or death will be recorded on the eCRF.

The Clinical Frailty Scale (CFS) [[R20-2080](#)] will be determined at the time point indicated on the [Flow Chart](#). The CFS is a means of summarising the overall level of fitness or frailty of an individual. It comprises a 9-point scale with categories ranging from 1 (very fit) to 9 (terminally ill).

5.2 ASSESSMENT OF SAFETY

5.2.1 Physical examination

A complete physical examination, including an assessment of presenting symptoms, will be performed at the time points specified in the [Flow Chart](#). It includes at a minimum general appearance, neck, lungs, cardiovascular system, abdomen, extremities, and skin.

Height and weight will be recorded at screening.

The results must be included in the source documents available at the site.

5.2.2 Vital signs and blood gases

Vital signs and blood gases will be evaluated at the time points specified in the [Flow Chart](#), prior to study drug administration as applicable.

Temperature, pulse rate, blood pressure, and respiratory rate will be assessed. SpO₂ will also be assessed. The results must be included in the source documents available at the site.

Blood gases (oxygen and carbon dioxide), when available as part of routine care, and respiratory support will be recorded. FiO₂ will also be recorded.

Measurements will be taken in line with standard practices for the study centre.

5.2.3 Safety laboratory parameters

Safety laboratory parameters to be assessed are listed in [Table 5.2.3: 1](#). For the sampling time points please see the [Flow Chart](#). All analyses will be performed by a local hospital laboratory, the respective reference ranges will be provided in the ISF.

Patients do not have to be fasted for the blood sampling for the safety laboratory.

It is the responsibility of the investigator to evaluate the local laboratory results. Clinically relevant abnormal findings as judged by the investigator will be reported as adverse events (please refer to [Section 5.2.6](#)).

In case the criteria for hepatic injury are fulfilled, a number of additional measures will be performed (please see [Section 5.2.6.1](#) and the DILI Checklist provided in the ISF). The amount of blood taken from the patient concerned will be increased due to this additional sampling.

Proprietary confidential information © 2021 Boehringer Ingelheim International GmbH or one or more of its affiliated companies

The Chronic Kidney Disease-Epidemiology Collaboration (CKD-EPI) formula will be used to estimate eGFR (R12-1392) using serum creatinine in mg/dL (Conventional Unit)* [[R12-1392](#)]:

$$(eGFR = 141 \times \min(S_{Cr}/\kappa, 1)^\alpha \times \max(S_{Cr}/\kappa, 1)^{-1.209} \times 0.993^{Age} \times 1.018 \text{ [if female]} \times 1.159 \text{ [if Black]}),$$

where:

S_{Cr} is serum creatinine in mg/dL,

κ is 0.7 for females and 0.9 for males,

α is -0.329 for females and -0.411 for males,

min indicates the minimum of S_{Cr}/κ or 1, and

max indicates the maximum of S_{Cr}/κ or 1

The equation does not require weight because the results are reported normalized to 1.73 m² body surface area, which is an accepted average adult surface area.

Note * when serum creatinine is reported in SI unit (μmol/L), the value must be multiplied by 0.0113 to obtain the value in Conventional Unit (mg/dL).

Table 5.2.3: 1

Safety laboratory tests

| Laboratory Assessments | Parameters |
|------------------------|--|
| Haematology | Blood Typing (only at screening) Reticulocyte Count (absolute) Complete blood count: Red blood cell count (RBC) Haemoglobin (Hb) Haematocrit (Hct) Mean corpuscular volume White blood cell count including differential Platelet count |
| Coagulation | D-dimer test Fibrinogen Activated partial thromboplastin time (aPTT) Prothrombin time (PT) International Normalised Ratio (INR) Protein C (activity as well as antigen, if available) Plasminogen activator inhibitor-1 (PAI-1) (activity) |
| Clinical Chemistry | Potassium Sodium Calcium Magnesium Phosphate Alkaline phosphatase Bicarbonate Creatinine Creatine kinase (MB fraction) eGFR (estimated by the CKD-EPI formula) Glucose Total bilirubin Aspartate aminotransferase (AST) Alanine aminotransferase (ALT) Gamma-glutamyl transferase (GGT) C-reactive protein (regular test) Ferritin Triglycerides Lactate dehydrogenase (LDH) Troponin (I) |

5.2.4 **Electrocardiogram**

The 12-lead ECGs must be administered by a qualified technologist and results will be recorded as scheduled in the [Flow Chart](#). ECGs should be performed 0.5-4 hours after drug administration. The investigator or a designee will evaluate whether the ECG is normal or abnormal and assess clinical relevance. ECGs may be repeated for quality reasons and a repeated recording used for safety evaluation.

Additional ECGs may be recorded for safety reasons. Dated and signed printouts of ECG with findings should be documented in patient's medical record. The aggregate PR, QRS, QT, RR, QTcF, and QTcB interval data, as available, from the local ECG readout will be recorded in the eCRF for safety evaluation.

Clinically relevant abnormal findings will be reported either as baseline condition (if identified at the screening visit) or otherwise as AEs and will be followed up and/or treated as medically appropriate.

Refer to [Section 3.3.4.1](#) for treatment discontinuation criteria regarding QT prolongation.

5.2.5 **Other safety parameters**

Not applicable

5.2.6 **Assessment of adverse events**

5.2.6.1 Definitions of AEs

5.2.6.1.1 Adverse event

An AE is defined as any untoward medical occurrence in a patient or clinical investigation subject administered a medicinal product and which does not necessarily have to have a causal relationship with this treatment.

An AE can therefore be any unfavourable and unintended sign (including an abnormal laboratory finding), symptom, or disease temporally associated with the use of a medicinal product, whether or not considered related to the medicinal product.

The following should also be recorded as an AE in the CRF and BI SAE form (if applicable):

- Worsening of the underlying disease or of other pre-existing conditions.
- Changes in vital signs, ECG, physical examination and laboratory test results, if they are judged clinically relevant by the investigator.

If such abnormalities already exist prior to trial inclusion, they will be considered as baseline conditions and should be collected in the eCRF only.

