2.1.2 Primary endpoint(s)

- Patients alive and free of mechanical ventilation at Day 29

[figure not shown]

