5.2.6.1.2 Serious adverse event

A serious adverse event (SAE) is defined as any AE, which fulfils at least one of the following criteria:

- results in death,
- is life-threatening, which refers to an event in which the patient was at risk of death at the time of the event; it does not refer to an event that hypothetically might have caused death if more severe,
- requires inpatient hospitalisation or prolongation of existing hospitalisation
- results in persistent or significant disability or incapacity,
- is a congenital anomaly / birth defect,
- is deemed serious for any other reason if it is an important medical event when based on appropriate medical judgement which may jeopardise the patient and may require medical or surgical intervention to prevent one of the other outcomes listed in the above definitions. Examples of such events are intensive treatment in an emergency room or at home for allergic bronchospasm, blood dyscrasias or convulsions that do not result in hospitalisation or development of dependency or abuse.

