### **7.8.1 Adverse events**

Analyses of adverse events will be descriptive in nature. All analyses of AEs will be based on the number of patients with AEs and NOT on the number of AEs.

The analysis of AEs will be based on the concept of treatment emergent AEs. That means that all AEs occurring between first drug intake till - after last drug intake will be assigned to the randomised treatment. All AEs occurring before first drug intake will be assigned to 'screening' and all AEs occurring after last drug intake - will be assigned to 'follow-up' (for listings only). For details on the treatment definition, see Section 6.1.

According to ICH E3 (10), in addition to Deaths and Serious Adverse Events, 'other significant' AEs need to be listed in the clinical trial report. These will be any non-serious adverse event that led to an action taken with study drug (e.g. discontinuation or dose reduced or interrupted).

For further details on summarization of AE data, please refer to the guideline 'Handling and summarization of adverse event data for clinical trial reports and integrated summaries' ill:

An overall summary of adverse events will be presented.

The frequency of subjects with AEs will be summarised by treatment, primary system organ class and PT (mention MedDRA levels to be displayed in the tables). Separate tables will be provided for subjects with SAEs, AEs leading to treatment discontinuation, AEs of at least moderate severity and related AEs with significant non-serious adverse events

The system organ classes will be sorted by default alphabetically, PTs will be sorted by frequency (within SOC). Customized sorting orders may also be used based on trial needs, e.g. SOC sorted by frequency.

The following are considered as protocol-specified AESI:

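### The pooled AE and SAE patient counts mix COVID-19 progression with other events, and the visible plan has no count without progression

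*Protocol*

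**What the plan says.** Protocol 5.2.6.1.1 includes "Worsening of the underlying disease or of other pre-existing conditions" among the occurrences that must be recorded as an AE and, where applicable, on the SAE form. Protocol 5.2.6.1.2 then makes an AE serious if, among other criteria, it "results in death", is life-threatening, or "requires inpatient hospitalisation or prolongation of existing hospitalisation". All patients are inpatients on oxygen at entry. The primary endpoint in Protocol 2.1.2 is "Patients alive and free of mechanical ventilation at Day 29".

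On analysis, SAP 7.8.1 says "An overall summary of adverse events will be presented" and "The frequency of subjects with AEs will be summarised by treatment, primary system organ class and PT". It adds "Separate tables will be provided for subjects with SAEs, AEs leading to treatment discontinuation, AEs of at least moderate severity and related AEs". The unit is the patient: "All analyses of AEs will be based on the number of patients with AEs and NOT on the number of AEs". SAP 7.8.5 adds a table of five kinds of extrapulmonary organ failure. Nothing in the visible text exempts efficacy outcomes from AE recording or plans a patient count without COVID-19 progression.

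**The concern.** Safety is part of the main objective (Protocol 2.1.1), and Protocol 1.4 expects no specific drug-related risk. Any toxicity would then be unexpected and might be spread thinly over several terms. A pooled patient count is the natural place to see such a pattern. Here that count also contains COVID-19 deaths and deteriorations, which the drug is meant to reduce. If it does reduce them, the fall can offset a rise in other serious events. If it does not, a shared background of disease events dilutes the rise, because a second event in a patient already counted adds nothing.

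**Working it through.** **Step 1: can the planned tables be taken apart?** Preferred-term rows count patients per term, and one patient can appear in several rows. Suppose two non-progression terms have 4 and 3 patients. The number of patients with at least one of them then lies anywhere from 4 (full overlap) to 7 (no overlap). The overlap with progression terms is equally unknown. The rows therefore do not give the number of patients with at least one non-progression event.

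**Step 2: how far could the pooled count mislead?** The plan states no AE or SAE figure to reproduce, and the body of Protocol 7.5 is not available. Only the arm size, 65 (Protocol synopsis), comes from the documents. All rates below are assumptions. Let c be the risk of a COVID-progression SAE and o the risk of any other SAE. If the two are independent, P(any SAE) = 1 − (1 − c)(1 − o).

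For the first row of the table:
- Placebo: 1 − 0.75 × 0.92 = 0.310.
- Active: 1 − 0.85 × 0.84 = 0.286.

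| c, placebo/active (%) | o, placebo/active (%) | Any SAE, placebo (%) | Any SAE, active (%) | Pooled difference (points) | True difference in other SAEs (points) |
|---|---|---|---|---|---|
| 25/15 | 8/16 | 31.0 | 28.6 | −2.4 | +8 |
| 20/12 | 6/12 | 24.8 | 22.6 | −2.2 | +6 |
| 30/20 | 10/20 | 37.0 | 36.0 | −1.0 | +10 |
| 25/25 | 8/16 | 31.0 | 37.0 | +6.0 | +8 |
| 20/20 | 6/12 | 24.8 | 29.6 | +4.8 | +6 |
| 30/30 | 10/20 | 37.0 | 44.0 | +7.0 | +10 |

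The first three rows assume an effective drug; the last three assume no efficacy. With no efficacy, 6.0/8 = 75%, 4.8/6 = 80% and 7.0/10 = 70% of the true excess stays visible.

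A wider range, with other SAEs at 5% versus 15% (true excess +10 points), shows how the result depends on efficacy:
- Progression SAEs 15% versus 10%: 19.25% versus 23.5%, a pooled difference of +4.25 points.
- Progression SAEs 25% versus 15%: 28.75% versus 27.75%, −1.0 point.
- Progression SAEs 35% versus 20%: 38.25% versus 32.0%, −6.25 points.

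**Step 3: break-even.** The pooled difference is zero when c(active) = 1 − (1 − c(placebo))(1 − o(placebo))/(1 − o(active)). For 25% progression on placebo and other SAEs at 8% versus 16%, this is 1 − 0.69/0.84 = 17.9%, a reduction of 7.1 points. For a 10-point excess (5% versus 15%, or 10% versus 20%) and placebo progression of 15% to 35%, the reduction needed is about 8 to 11 points.

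**Step 4: does independence drive this?** In the first row of the table, wholly separate events give 25 + 8 = 33% versus 15 + 16 = 31%. Full nesting gives 25% versus 16%. The active arm has the lower pooled count either way.

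**Step 5: precision of a separated count.** For 8% versus 16% with 65 per arm, the 95% half-width is 1.96 × √[(0.08 × 0.92 + 0.16 × 0.84)/65] = 1.96 × √0.0032 = 11.1 points. The excess itself is about 5 patients (65 × 0.08 = 5.2).

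**The case against.** A reader might infer that the AE and SAE tables largely repeat the efficacy result. The documents do not support that. They give no event rates. The primary endpoint is status at Day 29 (Protocol 5.1.1), so a patient intubated and extubated earlier is a responder who may still have an SAE. AE analysis ends with the residual effect period (Protocol 7.2.5), and collection narrows after the first follow-up visit (5.2.6.2.1). A patient who stops treatment early and later dies of COVID-19 before Day 29 may therefore fail the endpoint without entering these tables. AEs also include events unrelated to COVID-19.

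A reader might also infer that real toxicity would be hidden. That goes too far. SAP 7.8.1 plans a table of related AEs, and Protocol 7.2.5 tabulates causal relationship by system organ class and preferred term, with investigators blinded. The term-level rows, the laboratory-defined hepatic AESI, the laboratory, vital-sign and ECG summaries and the organ-failure table all remain, and the DMC sees both safety and efficacy data (8.7). These safeguards stand, but only in part: causality is a judgement in which underlying disease counts against the drug (5.2.6.1.6), and COVID-19 can itself affect organ failure and laboratory values.

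Further objections also have weight. The offsetting scenarios pair a rise in other SAEs with a sizeable fall in progression. Safety is descriptive, and no visible rule acts on the pooled SAE count. A net fall in all SAEs is a legitimate benefit-risk result. Worsening fills the discontinuation table only where treatment is actually stopped because of it; intubation is not a named stopping reason in 3.3.4.1, and nasogastric dosing is provided for. Finally, the AE guideline cited in SAP 7.8.1, the DMC charter and the redacted text were not available and could contain a split. Patient-level data would allow one later, though without prespecification.

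**Conclusion.** The point holds for the pooled patient counts: any AE, any SAE and AEs of at least moderate severity. That they mix progression with other events follows from the text and needs no assumption about rates. The size does rest on assumed rates. Under those shown, a moderate to large reduction in progression could cancel or slightly reverse a doubling of other SAEs in the total, while with no efficacy 70% to 80% of the excess would still be seen. Recording worsening as an AE is not an error. For an exploratory, descriptive trial of 130 patients this is a minor reporting gap, and closing it is an optional improvement. Even a separated count would be imprecise.

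**What to change.** In SAP 7.8.1, specify that a list of preferred terms denoting COVID-19 progression is fixed at one of the blinded report planning meetings already foreseen in SAP 6.2. That meeting should precede the release of treatment information described in SAP section 8, which comes before the final data lock. To the planned overall AE, SAE and severity summaries, add by arm the number of patients with at least one event outside the list. Keep every all-events table, and leave AE recording and reporting unchanged.

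The cost is one blinded list and a small set of extra rows or tables. The list involves judgement, and a respiratory toxicity coded to a listed term would appear only in the all-events tables, which is why those must stay. If the cited AE guideline already contains such a split, a cross-reference in SAP 7.8.1 would be enough.
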